**HH CONTACTS COHORT**

- i. Presence of a medical condition that, in the investigator's opinion, would interfere with the individual's participation or interpretation of results
- ii. Children weighing less than 5kgs
- iii. Clinical signs or symptoms of active TB (persistent cough, draining lymph node or other evidence of extra-pulmonary TB, fever, weight loss or failure to thrive (children), fatigue or lethargy, night sweats, pleuritic chest pain, or hemoptysis). If clinical signs or symptoms of TB are present but CXR, sputum culture and other evaluation rules-out TB, the participant may be enrolled
- iv. Not staying in the area for the duration of the study/plans to move away

**CONTROL COHORT**

- i. Presence of a medical condition that, in the investigator's opinion, would interfere with the individual's participation or interpretation of results
- ii. Children weighing less than 5kgs
- iii. Not staying in the area for the duration of the study/plans to move away

## 6. STUDY PROCEDURES

### 6.1. SCREENING

#### Recruitment of Active TB Cohort

A study counselor or nurse will determine if each patient identified at the two study sites, meets the inclusion criteria for the Active TB Cohort study. Patients who fulfill the inclusion criteria will be invited to participate in the Active TB Cohort. Details of the study, including study objectives and outcomes, will be explained to the patients in their native language and they will be asked to provide informed written consent prior to initiation of screening procedures. Informed consent of legal guardians and assent of the child will be obtained for participants under the age of 18 years. All participants will also be asked to provide home visit consent and agree to reveal their TB status to family members for the potential recruitment of participants for the Household Contacts Cohort. The timing of all follow up visits for the study participant from Cohort A is timed from the initiation of their TB treatment

#### Recruitment of Household Contact Cohort

An outreach team (eg- clinician, counselor and field investigator) will approach all participants enrolled in the Active TB Cohort for the potential enrollment of family members in the Household Contact Cohort. A household contact investigation among its members will be conducted only if the index case of the household had consented to the home visit and enrolment of their family members into the study. Enrollment of a household contact will occur within two weeks to 2months of the index case from Cohort A. Individual household members will be consented for the study procedures at the initial visit at their homes. The RNTCP nurse, PHC staff or the DOTS provider who supervises the TB treatment of the index case will support and participate in community education and awareness of the study and in recruitment of household contacts of the index case. A trained outreach team comprised of a study physician, nurse and counselor will go to the home to consent patients.

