#### **For HH contacts cohort**

A *10-item questionnaire* recently developed in South Africa that quantifies TB exposure as a reliable surrogate measure of TB infection in children will be administered [55]. All symptomatic HH contacts will be referred immediately to the clinical facility for further evaluation. Isoniazid Preventive Therapy (IPT) will be recommended for all asymptomatic children under age 5.

Assessments may happen at the home, mobile van, at the study clinic or some combination of the above based on the HH contact preferences.

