**F=Facilities-based activity; (F)= Facility Based activity only if indicated; H= Home-based activity; M=months**

 Any person who has active TB (prevalent or incident) is eligible for the Active TB Cohort if he or she consents. Active TB assessment will otherwise be done as included in this SOE if the participant does not enroll in the Active Cohort.

 All symptomatic household contacts will be referred immediately to the clinical facility for further evaluation. IPT will be recommended for all asymptomatic children under age 6 and all asymptomatic HIV+ household contacts

 Household food insecurity and dietary questionnaire

 Height, mid upper arm circumference, weight at baseline; at post entry visits, weight will be measured

 TST and QGIT will only be done if prior was negative

 HIV testing will only be done on adults. If there is a HIV+ adult in the household, then the legal guardian of the child will be asked if they want their child to be HIV tested

 Host mRNA, PBMC, saliva, will be performed on all at baseline and then a random subset of 200 households (n=800 contacts)

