Quantiferon Gold in Tube (QGIT): Approximately 3 mLs of blood will be collected and processed for QGIT in Active TB cohort participants at BL, , 4W, 8W, 6M, 12M, 24M, end of treatment and at recurrence; in HH cohort participants at BL, 4M, 12M, 24M, TB activation and in control cohort participants at BL, 4M and 12M.

HH Exposure to IAP: HH samples will be collected on a random subset to estimate air particle concentration (PM 2.5) and carbon monoxide as an objective marker for exposure to IAP from biomass fuels and corroborated with IAP questionnaire data.

Sample of hair: A small thatch of hair (~30-50 strands) will be collected for the hair sample.

For Active TB Cohort hair sample will be taken at BL, 4W, 5M, 6months, End of Tx and Recurrence;

For household contacts and controls: BL and 4 and 12 months.

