## 8. ASSESSMENT OF OUTCOME

*Aim 1: To examine the host and microbial factors associated with TB treatment outcomes*

- Primary outcome for Aim 1 will be a composite poor treatment outcome, defined as treatment failure, recurrence or death within 24 months of TB treatment initiation.
- Secondary outcomes will include time-to-sputum AFB negativity, time-to-culture negativity, and time-to-detection of MTB using liquid sputum culture on mycobacteria growth indicator tubes (MGIT).

*Aim 2: To investigate the host and microbial factors associated with the progression from infection to active TB disease*

- Primary outcome is incident TB within 24 months (best outcome to assess what factors are associated with the risk of progressing to active TB)
- Secondary outcome will be proportion with co-prevalent TB at time of initial household screening.

*Aim 3: To explore the host and microbial factors associated with MTB transmission*

- Primary outcome will be incident infection defined as conversion of TST or QGIT or at entry a positive TST (> 15mm) or QGIT in a child <5 years.
- Secondary outcome will be prevalent active TB at entry or incident TB among HH contacts that have the same DNA fingerprint using MIRU based genotyping at NIRT.

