The primary outcome is diagnosis of active TB among individual HH contacts within 24 months of follow-up. Index PTB cases from the Active TB Cohort will form clusters and individuals within the HH of the index case are correlated. The association between host and microbial factors with progression from infection to active TB disease will be estimated using random effects.

Poisson regression models with index PTB cases as random effects. Random effects models will address the correlation of individuals within the HH. Relative risk ratios and 95% confidence intervals for host and microbial factors will be estimated from the models and will have a cluster-specific interpretation.

**Aim 2 Power.** We expect approximately 3200 HH contacts will be followed for an average duration of 2 years. We anticipate 85% (n=2720) of them will be HH contacts of a smear positive PTB case, 15% (n=480) will be contacts of a smear negative PTB. We estimate that at least 40% (n=1280) will be latently infected. We estimate that 320 (25%) of them would be recently infected and have a 15% 2 year risk of developing active TB. This would result in 48 active TB cases. We expect a background rate of active TB (regardless of latent TB infection) 0.37% per year, yielding an additional 24 cases. This yields an estimated 72 incident active TB cases.

**Aim 3.** The analysis set will be HH members of index PTB cases.

Primary outcome will be incident infection will be defined as positive TST or QGIT in children < 5 years or seroconversion of TST or QGIT among HH contacts. Secondary outcome will be prevalent or active TB with same MTB MIRU genotype.

Within household transmission rates will be calculated. Risk factor and covariate information collected on HH contacts will be used in the analysis. In addition the analysis will be adjusted for independent variables measured at HH level. A multivariate random effects Poisson regression model will be used to estimate the adjusted relative risk of MTB transmission to HH contacts in presence of host and microbial factors. The model will be adjusted for enrollment site (NIRT & BJMC).

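### For contacts aged 5 or over, a recent household infection is more likely to count as an Aim 3 conversion when the baseline TST/QGIT is early in the two-week to two-month entry window, and the Aim 3 model names no term for that delay

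*Protocol*

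**What the plan says.** - **Entry window** (6.1, Recruitment of Household Contact Cohort): "Enrollment of a household contact will occur within two weeks to 2months of the index case from Cohort A". The event in the index case (diagnosis, enrolment or treatment start) is not named. For Cohort A, by contrast, 6.1 times follow-up visits from the start of treatment.
- **First contact** (same section): "Individual household members will be consented for the study procedures at the initial visit at their homes". No earlier test of contacts is described.
- **Test times** (6.3): QGIT is done "in HH cohort participants at BL, 4M, 12M, 24M, TB activation". Table 2 schedules the TST at entry, 4M, 12M and 24M as well.
- **Who is retested** (Table 2, footnote 5): "TST and QGIT will only be done if prior was negative".
- **Aim 3 primary outcome** (section 8): "incident infection defined as conversion of TST or QGIT or at entry a positive TST (> 15mm) or QGIT in a child <5 years". Section 9.1 keeps this structure without the 15 mm cut-off.
- **Aim 3 model** (9.1): a random-effects Poisson model using contact-level risk factors and covariates and household-level variables, neither of them listed. One adjustment is specific: "The model will be adjusted for enrollment site (NIRT & BJMC". No delay term, stratification by delay or common time origin is stated.

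**The concern.** TST and QGIT turn positive some time after infection. Take a contact aged 5 or over who was infected shortly before the index case started treatment. Tested at two weeks, this contact may still be negative, is retested at 4M, turns positive and is an Aim 3 event. Tested at two months, the same contact is more likely to be positive already, is not retested on that test, and is not an event on it. The infection is the same and only the visit date differs.

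Aim 3 looks for factors associated with transmission. If a factor under study also goes with later household visits, it will appear to lower transmission. If delay is unrelated to the factors, the estimated within-household transmission rate still depends partly on visit logistics, and precision suffers.

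**Working it through.** The protocol gives no event count, sample size or power for Aim 3, so there is no stated figure to reproduce. The check is an illustration of size.

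**Inputs from the protocol**
- Entry delay d: two weeks to two months, taken as 14 to 60 days.
- Exposure period that defines a contact: three months before index diagnosis (5.2), taken as 90 days.
- Aim 2 figures (9.1): 3,200 contacts; 40% latently infected = 1,280; 25% of these recently infected = 320. Uninfected: 3,200 − 1,280 = 1,920.

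**Assumptions, not in the protocol**
- Index diagnosis, enrolment and treatment start coincide.
- Infection times are uniform over the 90 days before that date.
- The lag L from infection to a positive test is uniform on 2-8 weeks, with 3-6 and 2-12 weeks as alternatives.

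**Step 1. Share still negative at baseline.** An infection t days before treatment start is still negative at baseline if L > t + d. The share is E[max(0, L − d)] / 90.

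For L on 14-56 days:
- d = 14: mean of L − 14 is 21 days; 21/90 = 23%.
- d = 28: (28² / 2) / 42 = 9.33; 9.33/90 = 10%.
- d = 42: (14² / 2) / 42 = 2.33; 2.33/90 = 3%.
- d = 60: 0, because the longest lag is 56 days.

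| Assumed lag | 14 days | 28 days | 42 days | 60 days |
|---|---|---|---|---|
| 3-6 weeks | 19% | 5% | 0% | 0% |
| 2-8 weeks | 23% | 10% | 3% | 0% |
| 2-12 weeks | 39% | 25% | 14% | 5% |

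**Step 2. Sensitivity to the infection-time assumption** (lag 2-8 weeks, baseline at two weeks). If infections fall only in the last 6 weeks, 21/42 = 50%. If they spread over 26 weeks, 21/182 = 11.5%. Both fall to 0% at two months. The size changes and the direction does not.

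**Step 3. Effect on total conversions.** Step 1 covers recent infections only. Conversions found at 12M and 24M from later infection hardly depend on the baseline date. As a rough scale, place all 320 recently infected contacts in the 90-day period, treat them all as aged 5 or over, and assume an annual infection risk of 2% or 5% in the 1,920 uninfected.
- Later conversions over two years: 1,920 × (1 − 0.98²) = 76, or 1,920 × (1 − 0.95²) = 187.
- Added at d = 14: 320 × 0.233 = 75. At d = 28: 320 × 0.104 = 33. At d = 60: 0.
- 14 against 60 days: 151 against 76 (2.0-fold), or 262 against 187 (1.4-fold).
- 14 against 28 days: 151 against 109 (1.4-fold), or 262 against 220 (1.2-fold).

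The 14-against-60-day figures compare everyone tested at one end of the window with everyone tested at the other, so within these assumptions they mark an extreme.

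**The case against.** **The model may already allow for delay.** Section 9.1 leaves its contact-level and household-level covariates open. Delay is largely a household-level variable and can be derived, because the study number links each contact to the index case (12.1). A reader might infer that the model ignores delay. The protocol shows only that it names none, and an unseen analysis plan could add it. This stands, but the wide window, the unnamed anchor and the rule that an entry positive does not count from age 5 are fixed here.

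**Bias needs an association.** No passage documents a link between delay and alcohol use, socio-economic status or disease severity. Site adjustment absorbs a difference between sites, and the household random effect absorbs some of the variation. This stands in part: neither removes bias if delay and a studied factor are associated within a site. A reader might also infer that slow consent by the index case drives the delay. The protocol largely designs that out: home visits are an inclusion criterion (5.2), refusing enrolment of contacts is an exclusion criterion (5.3), and home-visit consent is sought at index recruitment (6.1).

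**The effect on the whole outcome is diluted.** A reader might infer from the 90-day shares that total incident infection differs several-fold with visit date. It does not follow. Step 3 gives about 1.4- to 2-fold at the extremes under favourable assumptions. Children under 5 are largely unaffected, because their positive entry tests count anyway. A contact positive on one test and negative on the other at entry may still convert on the second.

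**No conflict with the referral rule.** Section 6.2 says "All symptomatic HH contacts will be referred immediately to the clinical facility for further evaluation". A reader might see a contradiction with an entry visit up to two months later. That rule says what follows once symptoms are found and is compatible with any enrolment date.

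**Conclusion.** The point holds for contacts aged 5 or over. Entry timing, retesting of negatives only, and the age limit on counting entry positives together make the Aim 3 primary outcome depend partly on when the household was visited. The direction needs only that positivity lags infection. The size rests on a lag and an infection-time distribution that the protocol does not give: about 19-39% of infections from the 90 days before index treatment still negative at 14 days, against 0-5% at 60 days, with a smaller effect on all conversions to 24 months. Distortion of the risk ratios is conditional on delay being associated with a studied factor within site. Without that, the consequence is a transmission rate that depends on logistics and some loss of precision. This is an improvable weakness in the design and analysis, and it does not invalidate Aim 3.

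**What to change.** 1. In 6.1, name the index date from which the two-week and two-month limits run, for example treatment start, which already anchors Cohort A visits.
2. In 9.1, Aim 3, include days from index treatment start to the contact's baseline test as a covariate, or report a sensitivity analysis by early and late baseline in contacts aged 5 or over. Fix the cut between early and late before the data are examined.
3. Report conversions found at 4M separately from later ones, since the dependence on baseline date should be concentrated there.

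The inputs are the index treatment start and contact baseline test dates, which the study number links. The cost is one sentence in 6.1, one model parameter and one table. No sample-size figure changes, because Aim 3 states none.

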#### Recruitment in Control Cohort

Control HH's will be randomly selected from within 5 km of the same communities as HH Contact Cohort using computer software such as the E-Pop. Assistance of Non-governmental organizations (NGO) working for TB will be sought for the enrollment of control HH's by establishing a networking system. A trained outreach team comprised of a study physician, nurse and counselor will go to the home to consent patients. For those patients who consent to participate in the study and specimen storage; baseline demographic and clinical data and specimens will be collected in the mobile van or in the clinic. Sample size =100 Households

## 6.2. CLINICAL ASSESSMENTS

### **For all 3 cohorts**

*Medical and Medication History:* All prior TB, HIV related events, diseases of the liver, lung (e.g. asthma/COPD, pneumonia), cardiovascular system, DM, and other immunosuppressive conditions will be recorded. Medication allergies and medication history including all prescription and nonprescription medications (e.g. any Ayurvedic, Unani, Siddha or homeopathy therapies) taken within 30 days prior to study entry will be obtained. Any prior medications for TB, HIV, DM will also be recorded. Children's co-morbidities (e.g. asthma, respiratory infections, HIV), and medications for chronic conditions will be collected.

*Socio-Demographic Form:* The detailed socio-demographic information about the Index and all the members of the household will be captured in this form. It includes information about the marital status, education, religion, employment status as well as the health seeking behavior of the Index cases as well as the individuals in the HH and Control Cohort. In addition, information about the socio-economic details about the family and TB source evaluation is also collected from the Index case. This form will be filled at the time of enrollment from the index as well as all the members of the household and the Control Cohort.

*Psychosocial Interview:* Interviews of all adult index cases and the adults in HH cohort will include alcohol use (AUDIT) [48], tobacco use behaviors (Fagerstrom) [49], illicit substance use, depression scale (CESD) [51]. For children a briefer interview will be conducted. Follow-up interviews will be conducted according to the evaluation schedule for each of the three cohorts.

*TB and Lung Health Assessment:* Signs/symptoms of TB at entry and at follow-up including cough, fever, night sweats, involuntary weight loss, and lymphadenopathy, and other lung health signs/symptoms (e.g., phlegm, wheezing, breathlessness) will be assessed using standardized questionnaires such as BOLD (or SGRQ) [52]. Follow-up Lung Health assessments will be conducted at every study visit.

*Concomitant Medications:* All medications including TB preventive treatment will be recorded at entry. Following entry visit, systemic medications started or stopped since the last study visit will be recorded on the case report form (CRF), including actual or estimated start dates and stop dates.

*IAP:* An assessment tool developed by IAP investigators at JHU will be used for IAP evaluations. Follow-up IAP evaluations will be conducted in the at the scheduled study visits for each cohort.

*Nutrition Assessment:* The HIFAS HH food insecurity questionnaire will be used for the assessment of nutritional status [54]. Follow-up assessments will be performed at the scheduled study visits.

*Targeted Physical Exam and Anthropometrics (post-entry evaluations):* This will include vital signs (temperature, blood pressure), height/length at baseline and weight. Exam will be driven by any previously identified or new signs/ symptoms experienced since the last visit.

Assessments may happen at the home, mobile van, at the study clinic or some combination of the above based on the HH contact and Control HH preferences. All assessments for the Active TB cohort will take place at the study clinic.

#### **For Active TB Cohorts alone**

The *relative impact of host factors* including age, sex, HIV, DM, tobacco exposure, IAP exposure, alcohol, BMI, mental health, presence of cavitation, and symptom duration on treatment failure will be assessed. EPTB adult cases and pediatric TB cases will be included for secondary analyses.

A *nested pharmacology study* to evaluate the relationship between exposures of first-line TB drugs and poor TB treatment outcomes of failure and recurrence will be conducted.

*Complete Physical Exam and Anthropometrics:* At entry this will include an examination of the vital signs (temperature, pulse, and blood pressure), height/length, weight, skin, head, mouth, neck, cardiac exam, abdominal exam, and lower extremities for edema.

*TB medication:* Type of TB regimen and self-report interviews on adherence to TB drugs using ACTG adherence questionnaire will be performed during treatment phase. Toxicity and response to treatment, adherence, time-to-AFB smear negative and culture negative status will be performed at consecutive follow-up visits.

*Diagnoses/Adverse events:* All diagnoses and adverse events (such as skin rash, numbness, tingling in extremities) identified by the treating clinician and/or visiting health worker will be recorded at follow-up visits.

All assessments for the Active TB cohort will happen at the study clinic.

#### **For HH contacts cohort**

A *10-item questionnaire* recently developed in South Africa that quantifies TB exposure as a reliable surrogate measure of TB infection in children will be administered [55]. All symptomatic HH contacts will be referred immediately to the clinical facility for further evaluation. Isoniazid Preventive Therapy (IPT) will be recommended for all asymptomatic children under age 5.

Assessments may happen at the home, mobile van, at the study clinic or some combination of the above based on the HH contact preferences.

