**TABLE 2. SCHEDULE OF EVALUATIONS FOR HH CONTACTS COHORT**

Time	Entry	4M	6M	12M	18M	24M	Active TB 
Consent/Enrollment	H						
Medical History	H						
Brief Psychosocial Interview	H			H		H	F
Brief Socio-demographic Interview	H						
Clinical Assessment  (i.e. TB and Lung Health Assessment, Concomitant Meds)/Medication History	H	H	H	H	H	H	F
Urine Pregnancy test	H	(H)					F
Nutrition Assessment 	H	H	H	H	H	H	F
IAP	H	H	H				
Targeted Physical Exam and Anthropometrics 	H	H	H	H	H	H	F
Chest radiograph	F	(F)					F
Sputum AFB and culture x 2 (DST if culture +)	H	H					F
TT Skin Test	H	H 		H 		H 	
Quantiferon Gold in Tube	H	H 		H 		H 	F
CBC	H						
Rapid HIV Test 	H						F
Hemoglobin A1c Point of care (Adults)	H			H			F
Household Air Sample (random subset)	H	H		H			
PFT (Adults), Spirometry (Child) (random subset)	H			H			
Samples for Biorepository							
Stored Plasma	H	H		H			F
Stored DNA	H						
Stored Sputum	H	H					F
Stored Urine	H	H		H			F
Stored Hair	H	H		H			F
Stored MTB isolate	H						F
Stored QGIT supernatant	H	H		H		H	F
Stored Host mRNA (Paxgene)	H	H 		H 			F
Stored PBMC	H	H 		H 			F

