Chest radiograph: CXR will be performed at baseline unless one was taken as a part of the clinical investigation of the participant's TB through the RNTCP. Data from an 8 week and 6 month CXR will be collected if testing was done as part of the RNTCP standard of care or if participant has pulmonary disease.

Pulmonary Function Tests/ Spirometry: Diagnosis of asthma/COPD will be performed on a random subset using portable PFTs (adults) and spirometry (children >5 years) to corroborate self-report as well as measure post-treatment lung health in Active TB Cohort and risk of development of TB in Contact Cohort.

Blood samples: Blood samples will be collected for storage and safety laboratory tests. Maximum of up to 28ml of blood will be taken from a vein for adults (age group >14 years) during study visits. Up to 20ml will be stored for future tests while remaining will be used for safety tests and CD4 counts. For children, the total volume of blood being collected shall not exceed 3ml/kg body weight in an 8 week period.

For storage -

For participants in the Active TB Cohort, samples will be taken at BL, 4 and 8W, 5M, 6M, 12 month, 24 months, end of treatment, and at recurrence.

For household contacts and controls, samples will be taken at BL and 4, 12 and 24 months.

For control cohort, samples will be taken at BL and 4, 12months.

For safety labs – following tests will be performed -

- a) Hematology: Complete Blood Count (CBC) with differential will be obtained for both all 3 cohort participants.
- b) HIV Studies: If HIV status is unknown, HIV testing will be performed on consenting adult participants. Children less than 18 years will only be tested for HIV if they are active TB cases or if a parent has tested positive or is known to be HIV-infected.
- c) Hemoglobin A1c for DM: Hemoglobin A1C, a recommended test for DM will be done for all adult participants of all three cohorts.
- d) Chemistry: Renal panel: Blood urea nitrogen (BUN), creatinine;  
*Liver Function Tests (LFTs):* Total bilirubin, AST, ALT, alkaline phosphatase and glucose.

Tuberculin Skin test (TST): A TST skin test will be placed and read ideally 48-72 hours (but within 1 week is acceptable) of placement on all HH contacts and controls. It will only be performed at follow-up visits if prior results were negative.

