## 9. STATISTICAL CONSIDERATIONS

### 9.1. SAMPLE SIZE AND ANALYSIS PLAN

**Aim 1.** The Active TB Cohort will include 800 adult PTB cases, 200 adult EPTB cases and 200 pediatric TB cases. The primary analysis set will be 800 adult PTB patients. Secondary analysis sets will include EPTB and pediatric TB.

Primary outcome is poor treatment outcome defined as failure, recurrence or death. Secondary outcomes will include time to AFB smear negativity, time to sputum culture negativity; time to detection of MGIT positivity. Host factors age, sex, DM, HIV, IAP exposure, tobacco exposure, malnutrition, and mental health will be key predictors for poor treatment outcomes.

Person-years of follow-up will be calculated for each member of the analysis set. Of TB patients who experience the outcome of interest, person-years of follow-up will be calculated as number of years between date of enrollment and date of event. Among those without the outcome person-years will be the number of years between enrollment and last date of follow-up. Crude treatment failure rates and 95% exact Poisson confidence intervals in the presence and absence of primary risk factors will be calculated. Adjusted treatment failure rate ratios will be estimated using multivariate Poisson regression models with person-years of follow-up as an offset. The Poisson regression models will also investigate interaction between individual and HH factors that might influence treatment outcomes.

A secondary subgroup analysis (may not be sufficiently powered) by enrollment sites, NIRT and BJMC, will be performed by adjusting the level of significance using a Bonferroni adjustment.

**Aim1 Power.** For Aim 1, we expect 20% (n=160) of 800 adult PTB cases will have the composite primary outcome (2% will fail, 6% will die, and 12% will have recurrence). This study will have at least 90% power at 5% level of significance to identify host and microbial risk factors (enumerated in section 3B3), with a prevalence of 10% - 40%, associated with poor treatment outcomes with relative risk ratio ranging from 1.5 to 6.0 over 24 months of follow-up.

**Aim 2.** The analysis set is individuals in the HH Contact Cohort: 3200 HH contacts of 800 PTB patients.

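### Isoniazid preventive therapy for household contacts has two age limits (under 5 in section 6.2, under 6 in Table 2 footnote 2), and section 6.2 omits the footnote's HIV-positive contacts

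*Protocol*

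**What the plan says.** Two places in the protocol say which household contacts (Cohort B) should be advised to take IPT.

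- **Section 6.2, For HH contacts cohort:** "Isoniazid Preventive Therapy (IPT) will be recommended for all asymptomatic children under age 5". HIV-positive contacts are not mentioned, and there is no reference to Table 2.
- **Table 2, footnote 2:** "IPT will be recommended for all asymptomatic children under age 6 and all asymptomatic HIV+ household contacts".

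In both places the rule directly follows the same instruction on symptomatic contacts. The footnote words that instruction as "All symptomatic household contacts will be referred immediately to the clinical facility for further evaluation", and section 6.2 differs only in abbreviating household to HH.

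Footnote 2 is attached to the Clinical Assessment row of Table 2 ("i.e. TB and Lung Health Assessment, Concomitant Meds)/Medication History"), which is scheduled at entry and at 4, 6, 12, 18 and 24 months.

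**The concern.** This is one rule written twice: same cohort, same drug, same condition of being asymptomatic, same commitment to recommend. Two age limits for one recommendation cannot both be the intended one. Both texts are current operating instructions; neither is background or a record of superseded wording. An analysis plan would not settle the matter, because it concerns what field staff tell participants.

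What is at stake is participant care. The protocol commits the study to recommending IPT; nowhere does it say that the study prescribes or supplies it. Staff who use Table 2 see the fuller rule. Staff who rely on section 6.2 could leave out an asymptomatic 5-year-old living with an adult who has pulmonary TB, or an asymptomatic HIV-positive contact aged 5 or over. With two sites each enrolling about half the sample, the sites could also apply different rules.

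**Working it through.** No sample size, power or event figure is involved, so the check is a comparison of texts.

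**Step 1: every statement on preventive treatment.** There are three: the section 6.2 rule, the Table 2 footnote 2 rule, and the Concomitant Medications paragraph of section 6.2. The third only says that preventive treatment is recorded at entry and later medication changes are recorded afterwards. It sets no eligibility rule, so it does not reconcile the other two.

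**Step 2: apply each rule to asymptomatic contacts.**

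| Asymptomatic contact | Section 6.2 | Table 2 footnote 2 | Result |
|---|---|---|---|
| Under 5, any HIV status | IPT recommended | IPT recommended | Agree |
| 5 to under 6, not known HIV-positive | Not named | IPT recommended | Age limits disagree |
| 5 to under 6, HIV-positive | Not named | IPT recommended on both grounds | Age limits disagree; HIV omitted |
| 6 or over, HIV-positive | Not named | IPT recommended | HIV omitted in 6.2 |
| 6 or over, not known HIV-positive | Not named | Not named | Agree |

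**Step 3: extent of the age disagreement.** 6 - 5 = 1 year of age.

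**Step 4: is the footnote a working instruction?** The row that carries it is marked as a home-based activity at entry, 4, 6, 12, 18 and 24 months, which is 6 scheduled visits. This shows that the footnote is in operational use. It does not measure the size of the discrepancy.

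**Step 5: would staff know who is HIV-positive?** Yes, in part. Table 2 schedules a rapid HIV test at entry. Footnote 6 says "HIV testing will only be done on adults", with an offer for children where an adult in the household is positive, and section 6.3 says "HIV testing will be performed on consenting adult participants" where status is unknown. For children, the section 6.2 history also covers HIV: "co-morbidities (e.g. asthma, respiratory infections, HIV), and medications for chronic conditions will be collected". The group that section 6.2 omits can therefore be identified at the visit.

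**Step 6: number affected.** The Aim 2 analysis set is "3200 HH contacts of 800 PTB patients". A count would need the share of contacts aged 5 and the share who are HIV-positive. The protocol gives neither, so no count is made.

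**The case against.** The strongest reply is that the two rules are nested and do not conflict. Section 6.2 does not restrict IPT to children under 5, so a site that recommends it to everyone under 6 and to every HIV-positive contact satisfies both texts. On this reading section 6.2 is merely the shorter statement. Harm then requires staff to work from the narrative alone, to read it as exclusive, and to meet a contact in one of the omitted groups, all for a measure that is only recommended.

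This reasoning is right for HIV, which is why that part is called an omission. It does not dispose of the age limit. A numerical cut-off is ordinarily read as the boundary of the rule, and a site following section 6.2 as written would have no instruction to recommend IPT to a 5-year-old. That the harm is narrow and conditional is accepted, and it keeps the point minor.

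A second objection also stands: the documents do not show which limit was meant. Elsewhere the protocol uses under 5 as its young-child cut-off (the Aim 3 infection outcome, gastric aspirates, specimen volumes in Table 4). Those uses do not concern IPT and do not settle the question, but they are a reason to have the clinical team confirm the limit before the text is changed.

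Finally, no analytical consequence should be read into this. Preventive treatment and later medication changes are to be recorded, and no bias in the Aim 2 or Aim 3 results is claimed.

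**Conclusion.** The inconsistency is real and the text is wrong as written. Two current statements of the same Cohort B rule give different age limits for children aged 5 to under 6, and section 6.2 leaves out the HIV-positive contacts whom footnote 2 includes. The first is a disagreement over one year of age; the second is an omission that following the footnote would cure.

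The severity is minor. The possible consequence is a missed recommendation to an individual participant, of unknown frequency. The conclusion rests on the two texts alone and needs no assumption about numbers. The only open matter is which age limit was intended.

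**What to change.** Subject to confirmation by the clinical team, replace the IPT sentence in section 6.2, For HH contacts cohort, with the wording of Table 2 footnote 2: "IPT will be recommended for all asymptomatic children under age 6 and all asymptomatic HIV+ household contacts". This version satisfies both existing texts and errs towards protecting the participant.

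If the team confirms under 5 instead, correct footnote 2 to that limit and still add the HIV-positive contacts to section 6.2. Either way, the age limit and the HIV rule should read identically in both places.

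The cost is one sentence in section 6.2 (plus one number in the footnote in the alternative case).
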